- NVivo (qualitative analysis software): The PIs will train research staff in NVivo. Additional NVivo resources are available here: <http://www.qsrinternational.com/learning>

Project Coordinator and Research Assistants

- EPIC (Needed for patient screening)
- Concept mapping method: The PIs will train research staff in concept mapping.
- Concept Systems Inc.: The PIs will train research staff how to use software needed for conducting analysis of concept mapping sessions. Concept mapping resources are available here: <http://www.conceptsystems.com/trainings/>

Additionally, the Jefferson Clinical Research Institute (JCRI) offers a full-day clinical research coordinator training and other periodic trainings on topics relevant to research staff. Updates are sent via the Office of Research Administration’s listserv: <https://lists.jefferson.edu/mailman/listinfo/ora.clinical>

B. PAKSAB members

i. General: All PAKSAB members will receive an orientation to the project, including its objectives, methods and key milestones involving the PAKSAB.

ii. Members serving as researchers will complete basic training as identified above, depending on role.

C. Data management plan

i. Data types, storage and person(s) responsible:

| Data | Storage | Person(s) Responsible |
|---|---|-----------------------------|
| Research team documents (agendas, minutes, draft materials for discussion, timeline, presentations, manuscripts) | Sharepoint (Web based secure file sharing system) | Research team |
| PAKSAB materials | Sharepoint; also disseminated by email | Project Coordinator, RA |
| Eligible participant lists | Selectrus (Imported from Epic) | IT, Project Coordinator, RA |
| Patient medical record | Epic | Project Coordinator, RA |
| Patient Tracker (name, MRN, date approached, date enrolled, interview/concept mapping date, study ID, type of data) | REDCap | Project Coordinator, RA |
| Ineligible/Refusal lists | One Drive (Web based secure file) | Research team |

| | | |
|--|---|----------------------------|
| | sharing system) | |
| Consent forms | Locked cabinet | Project Coordinator |
| Demographic forms | Locked cabinet | Project Coordinator |
| Interview audio recordings | One Drive | Project Coordinator |
| Interview transcripts | One Drive | Research team |
| Concept mapping data (statements, sorting, rating, maps) | Concept Systems Inc. software, web based platform | Research team |
| Time tracking | Excel spreadsheet on Sharepoint | Research team |

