2. Patients can come into the ED through “Fire Rescue” and are taken directly to the center desk.
 - First they are evaluated by the Senior Resident or Triage Nurse.
 - Then they are taken into a room or brought to a hallway bed.
 - A nurse registers them.
 - Then they receive formal triage
3. Patients can come into the emergency department and go straight into the Trauma Bay where they are actively worked on by the hospital staff.
4. After patients are in rooms (or hallway beds) and have been seen by the doctor it is determined which of several places they will go next:
 - Discharged home.
 - Placed in the Observation Unit.
 - Admitted to the hospital.
 - Transferred to another hospital or facility.

A ii. Screening process

Screening will take place during a random selection of days and times of day to ensure that we capture the full range of ED patients. Staff interviewers will sign up for three-hour shifts scattered on different days and at different times of day: morning, afternoon, evening, and night. Each PAKSAB interviewer will complete a minimum of two ED interviews. The research team will screen for eligible patients through the electronic medical record system. The research team uses a random generator to determine which patient to approach for enrollment, and will consult with the attending physician and nurse to determine the best time to approach the patient for enrollment.

Inclusion criteria

- Adult patient (age 18 and older)
- English speaking
- Capable of providing informed consent
- In the Jefferson Emergency Department (ED) for a type 1 or type 2 diabetes-related problem determined to require medical treatment: diabetic ketoacidosis, hypo/hyperglycemia, soft-tissue infections/cellulitis, neuropathy, retinopathy, acute renal failure, chest pain, and receiving diabetes medication refills.
- Patient has a less than fifty percent chance of being admitted to the hospital.

Exclusion criteria

- Patient is newly-diagnosed with diabetes
- Pregnancy
- Patient has had a significant permanent complication related to diabetes mellitus (DM) including:
 - End stage renal disease/on dialysis/history of kidney transplant
 - History of amputation
 - Blindness related to diabetes complication
- Patient undergoing medical clearance for a detox center or any involuntary court or magistrate order
- Patient in police custody or currently incarcerated individual

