Research staff members will complete JFMA interviews each week; PAKSAB interviewers will complete a minimum of two JFMA interviews over the course of the study. The research team will screen the schedule of upcoming appointments at JFMA, available through Selectrus, on Monday and Wednesday of each week and will identify potentially eligible patients for enrollment who have visits that week. Research team members will verify each patient's eligibility via EPIC, and may contact the patient's provider if any questions arise regarding the patient's eligibility for the study.

To identify potential JFMA interview participants

- Log in to Selectrus with your campus key and password
- The following are the data elements of this report:
 - Patient's MRN (EPIC)
 - Patient name
 - Patient's date of birth
 - Patient's age as of today (confirmed date calculation is correct)
 - Patient's phone number (only one available in the data)
 - ICD9 codes from list provided that are active in patient's record
 - ICD10 codes from list provided that are active in patient's record
 - Most recent A1c result
 - Date of most recent A1c result
 - Second most recent A1c result
 - Date of second most recent A1c result
 - Yes/no for two or more A1c results greater than 7.5 within the past year
 - Patient's next appointment date
 - Patient's next appointment time
 - Provider scheduled for patient's next appointment

- The following are the finalized specifications/inclusion criteria of this report:
 - Patients 18 years or older (as of today) who have an active diagnosis of diabetes on their problem list (ICD9 diagnosis of 250.XX OR ICD10 diagnosis of E11.XX or E10.XX), who have a HbA1c result ≥ 7.5 at least once within the past year and who have an appointment scheduled at the JFMA ([name]) location

Inclusion criteria

- Adult patient (age 18 and older) at JFMA ([name])
- Active diagnosis of type 1 or type 2 diabetes on problem list (ICD9 diagnosis of 250.XX OR ICD10 diagnosis of E11.XX or E10.XX)
- English speaking
- Capable of providing informed consent
- Scheduled for a routine follow-up visit at JFMA and has at least 1 measurement of HgbA1C > 7.5 in the prior year (with preference given to patients with 2 measurements of HgbA1C > 7.5 in the past year).

Exclusion criteria

- Pregnancy
- Patient has had a significant permanent complication related to DM including:
 - End stage renal disease/on dialysis/history of kidney transplant
 - History of amputation

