In addition to demographic data collected at the end of each interview, patient records will be reviewed by trained research personnel with use of the medical record number (MRN) to determine:

- Date of birth
- Information on hospital and outpatient utilization in the prior 12 months, including date of visit, location of visit (i.e primary care office, ED, inpatient), date of discharge if applicable, reason for visit, and discharge diagnosis
- Information on the visit associated with this study, including location of the visit, time and day of arrival, reason for visit, treatments provided, discharge diagnosis and instructions, and discharge disposition and time
- Insurance status (and provider, if applicable)
- Chronic medical conditions

All paper documents will be secured in locked cabinets in the Project Coordinator's office. Research team members will assign a Study ID to each participant and enter the Study ID, participant's medical record number and demographic information in the Patient Tracker, which is stored in REDCap. Interview transcripts will be labeled with the study ID number and sent to ADA Transcriptions. Once data analysis is complete, audio recordings of the interview files will be destroyed. The research team will import the transcripts into the analytic database (NVivo 11.0 software) for coding.

IV. Concept Mapping Session Protocol

i. Screening process

Individuals for the concept mapping groups will be screened from a list of potentially eligible patients made available through Selectrus. Patients will be called by a research team member two weeks before the first GCM session takes place. Up to three phone attempts may be made leading up to the GCM session to ask a patient if they are interested in participating. An equal distribution of patients from each care setting will be recruited.

To identify potential concept mapping participants

Acute care setting:

- The following are the data elements of the Selectrus report:
 - Patient's account number
 - Patient's MRN (EPIC)
 - Patient name
 - Patient's date of birth
 - Patient's age as of today (calculation corrected)
 - All available phone numbers for patient
 - Patient's ED admit date/time
 - Patient's ED discharge date/time
 - If the patient has not yet been discharged, field will be blank
 - Discharge disposition description
 - If the patient has not yet been discharged, field will be blank
 - Discharge Diagnoses

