 - If the patient's admit has not yet been coded, field will be blank
 - Name of where patient is discharged to
- The following are the finalized specifications/inclusion criteria of this report:
 - Patients aged 18 years or older (as of today) who have been admitted to the Jefferson ED

Note: the list will include patient who has had a visit to the Jefferson ED over the past 6 who has diabetes (with preference for those discharged in the last 3 months)

Post-acute care setting: Use Selectrus report procedure for post hospital discharge interviews with a filter for patients discharged from the JFMA/JIMA hospital service within the past 6 months. (page 11).

Primary care setting: Use Selectrus report procedure for JFMA interviews with a filter for patients who have had a routine scheduled office visit within the past 6 months (page 13)

Inclusion criteria

- Adult patient (age 18 and older)
- Active type 1 or type 2 diagnosis of diabetes on problem list (ICD9 diagnosis of 250.XX OR ICD10 diagnosis of E11.XX or E10.XX)
- English speaking
- Capable of providing informed consent
- *Acute care setting:* patient who has had a visit to the Jefferson ED over the past 6 months for a diabetes-related problem (with preference for those discharged in the last 3 months).
- *Post-acute care setting:* patient was discharged from the JFMA/JIMA hospital service within the past 6 months for a diabetes-related problem (with preference for those discharged in the last 3 months).
- *Primary care setting:* patient has had routine scheduled office visit within the past 6

months to the JFMA practice and has at least 1 measurement of HgbA1C > 7.5 in the prior year (with preference given for 2 measurements of HgbA1C>7.5 in the past year).

Exclusion Criteria

- Pregnancy
- Patient has had a significant permanent complication related to DM including:
 - End stage renal disease/on dialysis/history of kidney transplants
 - History of amputation
 - Blindness related to diabetes complication
- Patient undergoing medical clearance for a detox center or any involuntary court or magistrate order
- Patient in police custody or currently incarcerated individual
- Patient who has, in their clinician's best judgment, major communication barriers such as visual or hearing impairment or dementia that would compromise their ability to give written informed consent
- *Acute care and post-acute care settings*: Primary reason for admit is due to trauma or non-diabetes related health problem

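### The concept mapping criteria do not exclude people who already gave a VOICe interview, and no planned step would detect them; any resulting bias would tend to raise apparent coverage and is probably small

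*Combined protocol and SAP*

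**What the plan says.** Section IV.i gives the source of CM participants: "Individuals for the concept mapping groups will be screened from a list of potentially eligible patients made available through Selectrus". The three settings are handled as follows.

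- **Primary care:** "Use Selectrus report procedure for JFMA interviews with a filter for patients who have had a routine scheduled office visit", with a six-month window. The interviews in Section III.B ii used the appointment report: "The research team will screen the schedule of upcoming appointments at JFMA, available through Selectrus".
- **Post-acute:** "Use Selectrus report procedure for post hospital discharge interviews with a filter for patients discharged from the JFMA/JIMA hospital service", again with a six-month window.
- **Acute:** a Selectrus report of ED patients, the criterion being a "patient who has had a visit to the Jefferson ED over the past 6 months for a diabetes-related problem". ED interviewees were found differently, during the visit itself (Section III.A ii): "The research team will screen for eligible patients through the electronic medical record system".

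The CM exclusions cover pregnancy, permanent diabetic complications, detox clearance or court orders, custody, communication barriers and, for two settings, admissions unrelated to diabetes. Prior interview participation is not among them. Section IV.ii places each patient in one of the three CM groups but says nothing about keeping CM participants separate from interviewees.

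The means of checking already exist. Section II.C lists a "Patient Tracker (name, MRN, date approached, date enrolled, interview/concept mapping date, study ID, type of data", and Section III.D iii has staff enter each interviewee's "medical record number and demographic information in the Patient Tracker, which is stored in REDCap". No step uses this record to look for people who appear under both methods.

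**The concern.** Aim 2 asks whether CM elicits what interviews elicit, with interviews as the reference method. Section V.D answers descriptively, by the proportion of interview themes from each setting that are present in the CM list. That reading is cleanest when the two methods draw on different people. Someone who takes part in both is likely to raise similar outcomes twice, and may arrive at the CM session having rehearsed them in a 30-minute interview. Some of the agreement would then come from shared people and not from the method.

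The expected direction is upward, in favour of the method under test. The analysis would not show it. The selection-bias check in Section V.D compares enrolled patients with decliners on gender, race, ethnicity and age; it does not look for overlap. A repeat participant also receives a new CM study ID, with no stated link to the interview ID.

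**Working it through.** The manual states no sample-size or overlap figure, so there is none to reproduce.

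**1. Can an interviewee qualify?** Section I.C projects the last interviews for 3/31/2017. The CM dates in Section IV.ii carry no year; the milestones place them in 2017. Looking back six months from each group's first session:

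| First session | Six months earlier | Overlap with interview period |
|---|---|---|
| 9/23 | 3/23/2017 | 9 days (3/23 to 3/31) |
| 11/11 | 5/11/2017 | none |
| 12/2 | 6/2/2017 | none |

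Counting from the recruitment call two weeks before the first session (9/9, so back to 3/9) widens the 9 days to 23. Almost every interviewee would therefore need a new qualifying visit, and those interviewed early might also need a more recent high HbA1c. In primary care a new visit is plausible: Section III.B i gives about 35,000 patients and more than 80,000 visits a year, and 80,000 / 35,000 ≈ 2.3 visits per patient per year. It is less certain for ED and inpatient patients.

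**2. How many repeats in primary care?** Inputs:

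- Interviewees *I*: the total goal is 90-120 (Section I.C). An equal split by setting (assumption) gives 30-40.
- CM participants *C*: 16-20 per group, so 48-60 in three groups. Section IV.i asks for equal numbers by setting, which gives 16-20 primary care participants over all three groups.
- Pool *M*: not in the manual; values from 200 to 2,000 are assumed.
- Assumptions: every interviewee is still eligible, and everyone in the pool is equally likely to join.

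Expected repeats = *I* × *C* / *M*.

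| Pool *M* | 30 × 16 / *M* | 40 × 20 / *M* |
|---|---|---|
| 200 | 2.4 | 4.0 |
| 500 | 0.96 | 1.6 |
| 1,000 | 0.48 | 0.8 |
| 2,000 | 0.24 | 0.4 |

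These are totals over three groups. At a pool of 500 the figure per group is 0.96/3 to 1.6/3, or about 0.3-0.5. If all three settings had pools of the same size, the study totals would be three times the table: 7.2-12.0, 2.9-4.8, 1.4-2.4 and 0.7-1.2 of 48-60 participants.

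**3. What would that do to coverage?** An illustrative simulation used 40 themes mentioned independently, with each shared patient repeating the same themes and a single mention making a theme present. It compared 30 or 40 interviewees with 16, 20, 48 or 60 CM participants.

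| Shared CM participants | Rise in coverage, rare themes (1-5% prevalence) | Rise in coverage, mixed themes (1-30%) |
|---|---|---|
| about 10% | about 1-3 points | under 0.5 point |
| about 25% | about 3-7 points | under 1 point |

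At a pool of 500 in every setting, the shared fraction is 2.9/48 to 4.8/60, or 6-8%, which is below the first row. The simulation also placed all shared patients in the one interview set being compared; spread over three settings, the effect on each would be smaller. Rehearsal was not modelled and would act in the other direction.

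**The case against.** The strongest case against is that the overlap may be negligible and its effect diluted.

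- **Timing.** The six-month window removes nearly all interviewees unless they return for a new qualifying visit. This stands, and it makes the counts above upper-side for equal-chance calling.
- **One voice is enough.** A reader might infer that a single repeat participant can make a theme present and so change the result. The manual does not settle this. Section V.D compares final thematic clusters, and under Sections IV.iii and V.C these come from all participants' sorting and the group's majority decisions. The same section also speaks of a CM list, so a statement-level comparison is possible but cannot be assumed.
- **The same lists.** A reader might infer that both methods draw on identical lists. That is accurate only for the report procedures in primary and post-acute care, which are re-run with a later window. In acute care the population is shared, but the list is not.
- **Willing volunteers.** Past interviewees may be readier to join again, which would raise the counts. The manual gives no figure, so none is used.
- **Rules held elsewhere.** The IRB protocol, phone scripts and screening form are not reproduced and could contain such a rule. The manual describes the form only as a check of the exclusion criteria, which omit this one.

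These points limit the size of the problem. They do not supply the missing rule: staff following the manual exactly could enrol an interviewee and would not be asked to notice.

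**Conclusion.** The gap is real: nothing in the manual excludes interviewees from the CM groups, and no step detects or reports overlap. The expected direction is upward bias in the Aim 2 coverage proportion. The size cannot be derived from the manual and is probably small: in primary care, from about 0.2 expected repeats (pool of 2,000) to 4.0 (pool of 200) over all three groups, given equal-chance calling, an equal split of interviews by setting and full continuing eligibility. In the illustration, an overlap of about 10% moved coverage by no more than about 3 points. The material does not support saying that overlap will occur, or that agreement between the methods is an artefact of it. The change is still worth making, because the bias touches the primary comparison, favours the method under test and costs little to prevent.

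**What to change.** Add to the CM exclusion criteria in Section IV.i: *Completed a VOICe interview*. Before calling begins, match the CM lists by MRN against the REDCap Patient Tracker and remove the matches. If the screening form or phone scripts already contain this rule, a sentence saying so in Section IV.i is enough.

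The cost is one line and one lookup in a database the team already keeps. The calling list becomes slightly shorter, by at most 90-120 names.

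If a group has already met, count its repeat participants from the tracker and report the number per group as a limitation of the coverage result. Do not rely on deleting their statements. Section IV.iii has responses typed into one shared list with no contributor logged, and the clusters reflect everyone's sorting, so deletion would not undo their influence. Prevention before the sessions is much the better course.

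### The ED interview and concept mapping acute criteria select different patients, so a shortfall in the ED theme proportion could partly reflect who attended rather than the method

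*Combined protocol and SAP*

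**What the plan says.** For the ED interviews, Section III.A ii lists as an inclusion criterion: "Patient has a less than fifty percent chance of being admitted to the hospital". Section III.A v places the interview late in the ED visit or after discharge.

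For concept mapping, Section IV.i defines three settings by what happened in the previous 6 months:

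- Acute: "patient who has had a visit to the Jefferson ED over the past 6 months for a diabetes-related problem".
- Post-acute: "patient was discharged from the JFMA/JIMA hospital service within the past 6 months for a diabetes-related problem".
- Primary care: "patient has had routine scheduled office visit within the past 6" months at JFMA, plus at least one HgbA1C above 7.5 in the prior year.

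The Selectrus report for the acute setting is specified as "Patients aged 18 years or older (as of today) who have been admitted to the Jefferson ED", with a note narrowing it to patients with diabetes seen in the look-back period. Its data elements include "Discharge disposition description", but no rule uses that field. One exclusion is shared by the acute and post-acute settings: "Primary reason for admit is due to trauma or non-diabetes related health problem".

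On the mix of settings, Section IV.i states: "An equal distribution of patients from each care setting will be recruited". Section IV.ii adds that each group mixes the three settings, aims for 16-20 participants, and numbers participants by setting (100's, 200's, 300's). Section V.D then reports, for each interview setting, the proportion of its themes found in the CM list, first for the first CM group and then for all three groups combined.

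**The concern.** Section V.D gives the ED interviews their own coverage proportion, and comprehensiveness is the primary outcome (Section I.B). To read that proportion as a property of the method, the CM groups need people like those interviewed in the ED. The interview rule leans towards patients who go home from the ED. The CM rule does not, and admission is one of the ED outcomes listed in Section III.A i.

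If some acute places go to patients who were hospitalised, themes typical of the low-admission group have less chance of being raised. The gap would then be credited to concept mapping when part of it came from recruitment. The selection-bias check in Section V.D would not show this, because it compares enrolled patients with decliners on gender, race, ethnicity and age only.

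The same wording makes the settings overlap. A patient on more than one list has no stated place in the equal distribution.

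**Working it through.** **Comparing the criteria.** The plan gives no figure to reproduce, because the comparison in Section V.D is descriptive. The first check is on the wording.

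| | ED interviews (III.A ii) | CM acute setting (IV.i) |
|---|---|---|
| Reason for visit | Diabetes-related | Diabetes-related |
| Timing | Current ED visit | ED visit in past 6 months |
| Likelihood of admission | Under 50% (predicted) | No condition |
| Disposition | Not used as a criterion | In the report, not used |

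Take a patient who came to the ED with a diabetes-related problem, was admitted to the JFMA service and was discharged, all within 6 months. That patient meets the acute and the post-acute criteria from one episode. With a routine JFMA visit in the same window and one qualifying HgbA1C, the patient meets all three. Section IV.i does not say which list keeps such a patient.

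**Number of acute participants.** Equal thirds of 16-20 give 16/3 = 5.3 to 20/3 = 6.7 per group, so about 5 to 7. Over three groups the total is 16 to 20.

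**Could the low-admission group be missing altogether?** Let q be the share of eligible acute patients whose ED visit led to admission. The documents do not give q, so the values below are assumptions. With independent draws and n acute participants, the chance that none was treated without admission is q^n, and the expected number is n(1 − q).

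| q | Expected, n = 6 | Chance of none, n = 6 | Chance of none, n = 16 (three groups, low end) |
|---|---|---|---|
| 0.3 | 4.2 | 0.1% | below 0.1% |
| 0.5 | 3.0 | 1.6% | below 0.1% |
| 0.7 | 1.8 | 11.8% | 0.3% |
| 0.9 | 0.6 | 53.1% | 18.5% |

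Complete absence is unlikely unless q is high. Fewer such patients than intended is the realistic effect.

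**What could that do to coverage?** As an upper bound, assume a theme raised by 20% of patients treated without admission and by nobody else. The chance that at least one of n acute participants raises it is 1 − (1 − 0.2(1 − q))^n.

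| q | One group, n = 6 | Three groups, n = 18 |
|---|---|---|
| 0 | 1 − 0.80^6 = 74% | 1 − 0.80^18 = 98% |
| 0.3 | 1 − 0.86^6 = 60% | 1 − 0.86^18 = 93% |
| 0.5 | 1 − 0.90^6 = 47% | 1 − 0.90^18 = 85% |
| 0.7 | 1 − 0.94^6 = 31% | 1 − 0.94^18 = 67% |

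This bound credits nothing to the other two thirds of the group. If they miss the theme with probability m, every miss probability is multiplied by m. At q = 0.5 the one-group difference becomes (0.90^6 − 0.80^6) × m = (0.531 − 0.262) × m = 0.27m. The more the other participants share the theme, the smaller the effect.

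**The case against.** Much can be said for the plan as written.

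- A reader might infer that any ED visit qualifies. It does not: the visit must be diabetes-related.
- A reader might take the shared exclusion, with its reference to the reason for admission, as proof that hospitalised patients were meant to be acute. The manual also uses the word for arrival in the ED, as in the report specification, so the line proves nothing about intent. The mismatch rests on the missing disposition condition.
- The interview rule does not define a treat-and-release group. It is a predicted chance below 50%, so some interviewees may have been admitted. The two populations differ by degree.
- A reader might infer that setting is left wholly undefined. The three Selectrus procedures and the setting-numbered IDs suggest that setting follows the source list. What is missing is a rule for patients on several lists.
- A reader might infer that mislabelled settings distort the CM results. Section V.C makes the CM themes location-agnostic, so the theme lists do not depend on the labels. The matrices in Section V.D are exploratory, and no CM rows by setting are specified.
- The CM prompt asks what people with diabetes hope to change when they seek care and is not tied to a visit, so themes exclusive to one disposition are not to be expected.
- Section IV.vii collects 12-month utilisation, and the disposition of the associated visit, from the record. The actual mix can therefore be described afterwards.

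All of this narrows the point. It does not remove the difference between the two criteria or supply the missing rule for duplicates. Describing the mix afterwards would reveal an imbalance but could not recover themes that were never raised.

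**Conclusion.** The point holds in a limited form. The ED interview criterion and the CM acute criterion select different patients, and one ED episode can count as both acute and post-acute. The equal mix therefore does not secure the low-admission ED patients whose themes are being looked for. A low ED proportion could partly reflect attendance, chiefly against the first CM group, and much less once the three groups are pooled.

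The size cannot be fixed from the documents, because the admitted share, the amount of overlap between lists and the theme frequencies are all unstated. The fall from 74% to 47% in one group, and from 98% to 85% pooled, is a worst case resting on an assumed 20% theme frequency, an assumed 50% admitted share and no contribution from anyone else. It should not be read as an expected loss. Nor do the documents support saying that patients treated without admission would be absent: calls are made in random order, and at a 50% admitted share the chance of none among six is 1.6%.

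A change is worthwhile because it is cheap and removes an avoidable difference between the populations of the two methods.

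**What to change.** In Section IV.i, limit the CM acute list to diabetes-related ED visits in the past 6 months that did not end in hospital admission, using the disposition field already in the Selectrus report. State how observation-unit and transfer dispositions are handled, so that the list approximates the Section III.A ii criterion.

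The filter alone does not remove overlap with primary care or across separate episodes. Before the random call order is drawn, remove duplicates across the three lists by one prespecified rule, for example random assignment to one of the lists on which the patient appears. Apply the equal distribution and the 100/200/300 IDs to that assignment. The rule should not depend on the most recent encounter: Section III.C i says that patients discharged home are contacted to book an office follow-up, so such a rule could move post-acute patients into primary care.

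The cost is a few sentences in the manual, one filter, one de-duplication step and a somewhat smaller acute call list. The match to the interview criterion will be close but not exact, because that criterion uses a predicted chance of admission and the filter uses the actual disposition.
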